For all specific aims:

Prior to conducting any research related tests / procedures, the patient will be consented. The consent process will be facilitated by the IRB approved research coordinator and will occur in a private room in the pre-operative area prior to surgery. Once in the operating suite, the patient will be put under anesthesia for clinical purposes for surgery. Privacy will be maintained by limiting the individuals in the operating room to only necessary IRB approved research personnel. In addition, all data collected during the study will be immediately de-identified and stored on an encrypted, password protected server.

Behavioral Assessments. For each experiment, three behavioral responses will be evaluated: (1) loss/recovery of spontaneous movement (i.e., loss and recovery of responsiveness (LOR/ROR)) (2) loss/recovery of movement in response to stimuli (separately to clicks [non-salient] and verbal stimuli [salient], as per prior work by Purdon and colleagues⁴), and (3) loss/recovery of movement to command (verbal command with patient name with instruction to show different numbers of fingers, as proxy of loss/recovery of consciousness (LOC/ROC)). Stimuli will be presented in an interleaved fashion every 4 seconds binaurally via headphones (15 presentations of each stimuli at each dose, total 5 min per dose, or until failure to respond 3 times in a row to a certain stimulus). We use these separate measures because of the literature and our hypothesis that circuits mediating responsiveness and consciousness are separable. Namely, numerous studies highlight that consciousness (defined as ability to interact with the environment, most often measured by the isolated forearm test) can be maintained even with loss of responsiveness.^{39, 56}

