Surgeries are performed under monitored anesthesia care, using propofol anesthetic. Once patients are positioned, propofol is administered per a target-controlled infusion (TCI) anesthesia protocol detailed above. Participants will also complete the Behavioral Assessments outlined above. Assessment will be completed at the end of every propofol infusion (every 5 minutes). Blood draw will also occur at this time. If data is being collected for **Specific Aim 1**, no DBS stimulation will occur. If data is being collected for **Specific Aim 3a**, the patient will receive either GPi or GPe stimulation during study tasks. Once stable anesthesia is established, local anesthetic is infused and the generator is replaced, prior to closing the skin. Behavioral assessments will be made during induction and / or emergence.

Specific Aims 2 & 3b:

Data collection for these aims will occur during DBS implantation surgery. Data will be collected at UCLA and UTSW following the same protocol.

Surgical procedure Intraoperative Recordings (Specific Aim 2, 3). For DBS implantation for PD, the DBS lead is targeted to ventral posterolateral GPi using image-guided targeting (2-4 mm anterior, ¹⁹⁻²⁴ mm lateral, and 4-6 mm inferior to the mid-commissural point [MCP], Figure 4). All trajectories are confirmed with intraoperative microelectrode recordings, based on firing activity and kinesthetic tests⁵² in addition to intraoperative awake macrostimulation testing, clinically assessed by [name]. LFP will be recorded from deep brain targets from the DBS lead's four or eight contacts (dependent on clinical selection of DBS

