Behavioral data analysis and constructing propofol dose response curve. Behavioral data will be collected from both PD and ET patients undergoing generator replacement surgery. Propofol will be administered using a recently published, unified PK-PD for propofol developed to predict the BIS (bispectral index) response to propofol for a broad, diverse population by Eleveld and colleagues, which includes age adjustment, allometric scaling, and parameters for arterial and venous sampling.⁵⁷ (Although not a focus of our work and its value questionable given our underlying hypothesis of altered mesocircuit function in PD, we will record BIS in all patients as an additional data point.) From a range of studies, we expect that in a healthy population loss of responsiveness in 50% of healthy patients will occur with an age-adjusted effect site concentration (Ce₅₀) between 2.71–3.44 µg/ml.⁷⁴ The only published pharmacodynamic studies in PD patients reported a Ce₅₀ of 2.05 and 2.28 µg/ml.^{47, 48} We therefore expect that the dose-response curve for PD patients will be shifted to the left compared to ET patients, who lack basal ganglia pathology. To test this hypothesis, propofol infusion will be initiated with an effect-site concentration (Ce) target of 1.4 µg/ml for 5 min, incremented by 0.3 µg/ml steps every 5 min until loss of behavioral responses (as defined in 3.1.4). One additional incremental step will be performed after loss of responses. Venous serum samples will be drawn at the end of each 5 min step before the next increment. After conclusion of the procedure, target Ce would decrement by 0.3 µg/ml every 5 min until recovery of behavioral responses. Serum sampling will be used to confirm that the Eleveld unified TCI model is functioning as predicted.

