PK-PD Model Fitting. The pharmacodynamic responses for both behavioral endpoints will be modeled with a sigmoidal E_{max} function: $Fraction_{responsive} = 1 - C_e^{\gamma} / (C_{e50}^{\gamma} + C_e^{\gamma})$; Where Ce is the effect site concentration, Ce₅₀ is the effect site concentration at which half of the population is no longer responsive, and γ is the Hill coefficient governing the slope of the sigmoid. Fitting will be done using NONMEM (ICON Development Solutions) and parameter estimation. Comparison of Ce₅₀ values between PD and ET populations will be made using 95% confidence limits on the resulting parameter fits. Additional exploratory analyses of the model will attempt to account for heterogeneity in the PD population by constructing candidate models that nest the PD effect by both UPDRS scores and covariates of cognitive function (MoCA), utilizing a drop of corrected Akaike Information Criterion (AIC) by 20 points as a threshold for a significant improvement from adding a parameter to the model.

Specific Aim 2:

We will temporally correlate the evolution of behavioral measures of LOC/LOR (including loss of spontaneous movement and loss of movement to command, with digital synchronization with neurophysiological recordings through digital event recording) with I changes in GPi vs GPe pallidocortical circuits. Techniques outlined in LFP analyses above will be implemented to complete assessment.

Specific Aim 3a:

Statistical analysis pipeline outlined in Aim 1 will be replicated in Aim 3a.

Specific Aim 3b:

Recordings and behavioral assessments will be compared to results acquired in Aim 2. Techniques outlined in LFP analyses above will be implemented to complete assessment.

SAMPLE SIZE

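### The Aim 1 response curve fixes full responsiveness at zero drug and the PD-ET Ce50 comparison has no age term, so baseline motor deficit and age can be mixed with propofol sensitivity

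*Combined protocol and SAP*

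**What the plan says.** **Model.** Under Specific Aim 1, PK-PD Model Fitting: "The pharmacodynamic responses for both behavioral endpoints will be modeled with a sigmoidal" Emax function, beginning "Fraction_{responsive} = 1 - C_e" and continuing as Ce^γ/(Ce50^γ + Ce^γ). The only parameters are Ce50 and γ. PD and ET are compared by 95% confidence limits on Ce50.

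**Endpoints.** Behavioral Assessments lists spontaneous movement, movement to stimuli, and "loss/recovery of movement to command (verbal command with patient name with instruction to show different numbers of fingers" as the proxy for consciousness. Each stimulus is given 15 times per dose, "or until failure to respond 3 times in a row to a certain stimulus".

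**Conditions.** In Aim 1, "no DBS stimulation will occur". Under Specific Aim 1 of the data analysis, "propofol infusion will be initiated with an effect-site concentration (Ce) target of 1.4" µg/ml, rising by 0.3 every 5 minutes until responses are lost, plus one further step. On timing, the Specific Aims 1 & 3a section says: "Assessment will be completed at the end of every propofol infusion (every 5 minutes". Item 4.d counts 3-5 behavioral assessments, depending on the number of infusions. No assessment before drug is stated.

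**Age and covariates.** The dosing model is described as including age adjustment. The plan expects "loss of responsiveness in 50% of healthy patients will occur with an age-adjusted effect site concentration" of 2.71-3.44 µg/ml. The only covariates named for the response model are UPDRS and MoCA, in exploratory models of heterogeneity within PD.

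**Carry-over.** Aim 3a repeats the Aim 1 analysis and compares stimulated PD patients with the unstimulated PD patients from Aim 1.

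**The concern.** PD is both the exposure under study and a disorder of movement, and the readout is movement. A patient who misses some commands before any drug is given cannot be described by a curve that must start at 100%. The fit can absorb those misses only by moving Ce50 or flattening γ. Aim 1 reads a Ce50 difference as evidence that the basal ganglia regulate consciousness, so a shift produced by motor deficit would be misread.

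The groups are formed by diagnosis. If they differ in age and Ce50 varies with age, the unadjusted contrast carries that difference too. The exploratory UPDRS and MoCA models do not solve either problem: they act on the PD effect within PD, not on baseline response or on the PD-ET contrast.

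In Aim 3a, if stimulation changes the ability to move, baseline response would differ between the arms being compared.

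**Working it through.** **1. The plan's own figure.** The sample-size section assumes a 20% difference in Ce50, 20% intersubject variability and an additive error of unstated size, and obtains about 24 per arm. Without added error, n = 2(1.96 + 0.84)²(0.20/0.20)² = 15.7, so 16 per arm. A total SD of 0.247 gives 15.7 × (0.247/0.20)² = 23.9, so 24; this implies added error of √(0.247² − 0.20²) = 0.145. The 24 is attainable but cannot be confirmed. The planning simulation varied only Ce50, so it could not have revealed a baseline or age effect.

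**2. The constraint.** At Ce = 0 the Hill term is 0, so the modelled fraction is exactly 1.

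**3. Hand check of the motor effect.** If the truth is E0 × (1 − Hill term), half the presentations are answered where (Ce/Ce50)^γ = 2E0 − 1, that is at Ce50 × (2E0 − 1)^(1/γ). With E0 = 0.80 and γ = 5 (assumed), this is 0.6^0.2 = 0.90 of the true Ce50. The fitted value goes lower, to 0.85 with doses to 4.1, because misses at low doses also force the fitted γ down from 5 to 3.4.

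**4. Noise-free fit of the plan's curve.** True Ce50 is 2.71, the lower end of the plan's healthy range. Steps are 1.4, 1.7, and so on, equally weighted. Slopes and PD baselines are assumptions.

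| Top dose (µg/ml) | γ | E0 = 0.95 | 0.90 | 0.80 | 0.70 |
|---|---|---|---|---|---|
| 4.1 | 5 | 0.96 | 0.93 | 0.85 | 0.76 |
| 4.1 | 8.6 | 0.97 | 0.93 | 0.86 | 0.79 |
| 2.6 | 5 | 1.00 | 0.98 | 0.92 | 0.81 |
| 2.6 | 8.6 | 1.04 | 1.06 | 1.02 | 0.91 |

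Entries are apparent Ce50 divided by true Ce50. The 2.6 rows matter because five steps from 1.4 end at 1.4 + 4 × 0.3 = 2.6, and item 4.d counts at most five assessments. The Aim 1 text instead escalates until response is lost, so the range reached is uncertain.

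**5. Simulation at the planned size.** Assumptions: 24 per arm, equal true Ce50 of 2.71, 20% between-patient variability, 15 presentations per step to 4.1, pooled fit with patient-level robust standard errors, a 5% two-sided test on the Ce50 ratio, and 250 runs.

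| PD baseline | Plan's PD:ET ratio | Falsely PD more sensitive | Ratio with E0, Ce = 0 block and age |
|---|---|---|---|
| 1.00 | 1.00 | 1.6% | 1.00 |
| 0.95 | 0.97 | 9% | 1.00 |
| 0.90 | 0.94 | 19% | 1.00 |
| 0.80 | 0.86 | 78% | 1.00 |
| 0.70 | 0.79 | 99% | 0.99 |

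Total rejection with no bias present was 7% for the plan's model and 9% for the extended one, so small excesses should not be over-read. The extended model estimated E0 for PD only and had no patient random effect.

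**6. Age.** Assume Ce50 falls by 5% or 10% per decade and the groups differ by 7 years. If PD patients are older, the expected ratio is 0.95^0.7 = 0.96 or 0.90^0.7 = 0.93. If they are younger, it is 1/0.965 = 1.04 or 1/0.929 = 1.08. Simulation gave 0.96, 0.93, 1.04 and 1.09. With PD 7 years younger and 10% per decade, power for a true 20% difference fell from 96% to 66%; the age term restored 94%.

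**The case against.** **Direction is not fixed.** This stands. The 2.6 rows above show shrinkage and reversal. Fitting a mixed model to presentations cut off by the three-miss rule moved Ce50 up 8-11% at an assumed within-patient slope of 12, and by 0 to −7% at slope 6. A reader might infer that the motor bias always favours the hypothesis; the documents do not establish the dose range or data handling needed for that. The dependence of Ce50 on baseline movement remains.

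**The model may be meant per patient.** The plan defines Ce50 as the point where half the population is unresponsive, so each patient may simply be responsive or not at each step, and three consecutive misses absorb isolated ones. At a baseline of 0.90 the chance of a false run of three in 15 presentations is 1.2% per step and the apparent ratio is 0.98. At 0.80 and 0.70, however, the chances are 8.3% and 23.7%, and the ratios 0.87 and 0.68. The reading protects only when the deficit is mild.

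**Age is already handled.** Only in part: age enters the model that predicts and targets Ce, not the stated Ce50 comparison. A reader might also infer that any age difference makes PD look more sensitive. That requires PD patients to be older and Ce50 to fall with age, and the documents give neither group's age. Eligibility and matching text is not in the supplied document, so a lack of age matching cannot be asserted.

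**Other context.** ET patients are also tested off stimulation. BIS, which does not depend on movement, is recorded, but the plan treats it as an additional data point of questionable value.

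**Conclusion.** The concern holds in a limited form. The model fixes full responsiveness at zero drug, no drug-free assessment is stated for a movement-based endpoint in a movement disorder, and the non-randomized Ce50 comparison has no age term. With doses spanning the Ce50, an assumed PD drug-free response of 0.70-0.80 alone yields an apparent reduction of roughly 14-24%, comparable with the planned 20% effect. At 0.95 or above the reduction is about 3-4%. If doses end near 2.6 it can shrink or change sign. An age gap of 7 years, under the assumed slopes, shifts the ratio by about 4-9% in either direction.

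A reader might infer that Aim 1 would confirm its hypothesis from motor disability or age alone. The documents do not support that: they report no drug-free response rate in PD, and the size of the bias rests on that rate and on assumed slopes. The supported conclusion is that the planned analysis cannot separate these effects from propofol sensitivity, and that the data needed to do so cannot be collected after surgery.

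**What to change.** - Fit E0 × (1 − Hill term), with E0 estimated by group and a patient random effect. In Aim 3a, estimate E0 by stimulation arm.
- Inform E0 with one block of the existing headphone stimuli before the infusion starts, in every group.
- Prespecify age as a covariate on Ce50 in the primary PD-ET comparison, and keep UPDRS and MoCA exploratory.
- State whether the model is fitted to single presentations or to per-patient status at each step, and how presentations cut off by the three-miss rule are treated.
- Rerun the sample-size simulation with E0 and age included.

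Leave the loss-of-response rule that governs dose escalation unchanged; baseline response should be handled in the analysis only.

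The cost is a few extra parameters and a slightly wider Ce50 interval. In the simulation without additive error, power for a true 20% difference was about 95%, against 96% before. The block takes about 3-5 minutes: three stimulus types × 15 presentations × 4 seconds = 180 seconds, and the protocol allows 5 minutes per dose. Item 4.d already lists about 40 minutes of added operating time. Without the block, E0 would have to be inferred from the lowest doses and the assumed curve shape, which is weaker.

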Aim 1: We estimate our sample size using a Monte Carlo simulation based on predicted differences in propofol sensitivity as defined in prior studies,^{47, 48, 57, 75} which suggest a 20% difference in Ce50 with 20% intersubject variability and an additive measurement error. We performed the Monte Carlo simulation by constructing two population response curves from N patients whose response to propofol was determined by the sigmoidal Emax model while varying only the Ce50 between the populations. The nonlinear fitting was performed for both populations and this process was repeated 1000 times, with the fraction correctly identifying the underlying difference in the model used as our power estimate. N was then incremented until 80% power was obtained, which required approximately 24 patients per arm (total of 48 patients). Similar studies have targeted enrollments of 18-31 subjects per arm.^{47, 48, 76} To account for an estimated 20% dropout rate or protocol error, we plan to recruit a total of 58 subjects. All patients will be recruited from / data collection will occur at UCLA for Specific Aim 1.

Aim 2: Our experiments are purposefully designed to ensure proper power and that experiments can be completed within intraoperative time constraints. Using our prior LFP recordings in PD as well as the published literature^{43, 78, 79}, we conducted a power analysis based on average α/β power modulation between rest and anesthetized state observation (Figure 1). Power analysis indicates a total of 16 patients is required to achieve significant results (one-sample t-test with $d=0.75$, $p=0.8$, $\alpha=0.05$). To account for an estimated 20% dropout rate or protocol error, we plan to recruit at least 20 subjects. Data collection will occur at UTSW and UCLA.

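### The 20-point AICc threshold for adding UPDRS or MoCA does not measure a significant improvement: in a patient-level model of about 24 PD patients it has little power unless the covariate explains most of the Ce50 variance

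*Combined protocol and SAP*

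**What the plan says.** The rule is in section 4.a, Data Analysis, Specific Aim 1, under PK-PD Model Fitting. The purpose is described as "Additional exploratory analyses of the model will attempt to account for heterogeneity in the PD population", by building candidate models that "nest the PD effect by both UPDRS scores and covariates of cognitive function (MoCA"). The decision rule for each added parameter is given as "utilizing a drop of corrected Akaike Information Criterion (AIC) by 20 points as a threshold for a significant improvement". No reason is given for 20, and no power or error rate is given for the rule.

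On the model, the text says "Fitting will be done using NONMEM (ICON Development Solutions) and parameter estimation". It gives a population-level sigmoid Emax equation. It does not give the random effects, the unit of observation, or whether n in the AICc counts patients or responses.

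The main PD versus ET comparison of Ce50 follows a different rule: it "will be made using 95% confidence limits on the resulting parameter fits". The Aim 1 sample size, "which required approximately 24 patients per arm (total of 48 patients"), was set for that comparison. On recruitment the plan says "To account for an estimated 20% dropout rate or protocol error, we plan to recruit a total of 58 subjects". The Aim 1 pipeline is to be repeated in Aim 3a, so the threshold may carry over.

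**The concern.** AICc already charges a model for each added parameter. A required drop of 20 is a large further hurdle, yet the plan treats clearing it as the mark of significance. Two things are at stake.

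- In a patient-level fit of this size, a covariate with a real and sizeable relation to propofol sensitivity would usually fail. A gradient with motor severity or cognition within PD bears on the trial's hypothesis that basal ganglia pathology alters the response to propofol. A failed covariate could easily be misread as evidence against it.
- The meaning of 20 points depends on the likelihood, which the plan leaves open. If repeated responses from one patient are treated as independent, the same number can be reached by chance.

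**Working it through.** **Inputs.** From the plan: a 20-point AICc drop; one added parameter per step; about 24 PD patients; 58 recruited in total, so 58/2 = 29 PD patients if split equally with no loss; 20% between-patient variability in Ce50; Ce targets starting at 1.4 and rising by 0.3 µg/ml; up to 15 presentations per stimulus per dose. Assumed: a normally distributed covariate and, for the step-level simulations, a PD median Ce50 of 2.2 µg/ml (inside the 2.05-2.28 the plan cites), an SD of 0.20 on the log scale and a Hill coefficient of 8 or 15. The plan states no figure for this rule's performance, so there is none to reproduce. The 24 per arm is taken as given.

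**1. Convert the threshold to a likelihood-ratio statistic (LRT).** With K parameters, the AICc penalty is 2K + 2K(K+1)/(n-K-1). The LRT must be at least 20 plus the change in penalty. Going from 2 to 3 parameters (mean and variance, then a slope):

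- n=24: penalties 4 + 12/21 = 4.57 and 6 + 24/20 = 7.20, so LRT ≥ 20 + 2.63 = 22.63
- n=29: penalties 4 + 12/26 = 4.46 and 6 + 24/25 = 6.96, so LRT ≥ 20 + 2.50 = 22.50

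The chi-square tail on 1 degree of freedom is about 2e-6 in both. Other parameter counts, or a large n counted in observations, move the requirement only between 22.0 and 22.9.

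**2. Convert to variance explained.** For a patient-level covariate, the required observed R² is 1 - exp(-LRT/n):

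- n=24: 1 - exp(-22.63/24) = 0.61, or |r| about 0.78
- n=29: 1 - exp(-22.50/29) = 0.54, or |r| about 0.73

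These assume a fit to PD patients alone. If the variance is shared with the ET group, the required R² is about 0.75.

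**3. Chance of passing, best case.** Simulated with each patient's log Ce50 known exactly. The last column is an LRT cut of 6.63 (nominal p<0.01), for scale only.

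| True r (variance explained) | 20-point rule, n=24 | 20-point rule, n=29 | LRT > 6.63, n=24 / n=29 |
|---|---|---|---|
| 0.5 (25%) | 1.3% | 2.6% | 54% / 64% |
| 0.6 (36%) | 5.8% | 11% | 78% / 87% |
| 0.7 (49%) | 22% | 38% | 94% / 98% |
| 0.8 (64%) | 63% | 82% | not needed |
| 0.9 (81%) | 98% | 99.8% | not needed |

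With no effect, the 6.63 cut passes in about 1.4-1.5% of datasets. A test calibrated to exactly 1% would therefore have somewhat less power than the last column.

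**4. Mixed model on the protocol's dose steps, n=24** (100 to 150 runs per cell):

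- One response per step: passes in 0-1% at r=0.5, 1-11% at r=0.7 and 25-53% at r=0.9.
- 15 responses per step, Hill 15: 1%, 19% and 97%.

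**5. Pooled fit, 15 responses per step, no patient random effect, n=24.** With no covariate effect, the 20-point rule is met in 31-39% of datasets across repeated simulations. At r=0.5 it is met in 92-96%. A fixed LRT cut of 6.63 is passed in about 60% of null datasets under the same pooling.

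**The case against.** The strongest reply is that this is a deliberate, strict filter for choosing among several candidate models in about 24 patients, in an analysis labelled exploratory, and that strictness there is defensible. The exploratory label stands and limits the weight of the point. But the plan gives no reason for 20, and a filter that misses a covariate explaining 25-36% of the variance in about 89-99% of trials is ill suited to finding leads.

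A second reply is that the direction of the problem depends on a likelihood the plan does not state. That is right. NONMEM makes a mixed model plausible, but the text does not commit to one. This does not rescue the threshold: it is too strict in a patient-level fit and too lenient in a pooled one. It also means that swapping 20 for another fixed cut, such as 6.63, would not be safe.

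Two stronger readings are tempting and not supported:

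- A reader might infer that the analysis is bound to be negative whatever the truth. It is not: at r=0.8 the rule passes in 63-82% of trials, and at 0.9 in 98% or more, when Ce50 is well measured.
- A reader might infer that the plan will report a failed covariate as having no effect. It says neither that nor that coefficients go unreported; it sets only a rule for adding a parameter. The general statistical analysis paragraph also plans a regression relating behavioral and LFP metrics to UPDRS-III. That is partial cover, since it belongs to the LFP analyses and omits MoCA.

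**Conclusion.** The point holds for the exploratory PD heterogeneity analysis. The 20-point AICc rule does not measure a significant improvement. In a patient-level mixed model with 24 to 29 PD patients it has little power short of a covariate that explains most of the between-patient variance in Ce50. A negative result would then say little about heterogeneity. Under pooling of repeated responses, the rule would be met by chance in roughly a third of null datasets.

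The patient-level power figures rest on a PD-only fit, a normal covariate and exactly known Ce50. The figure for 29 patients also needs an equal split and no loss, against the plan's own 20% dropout. The pooled figure rests on the assumed Ce50, Hill coefficient and 15 responses per step. The primary PD versus ET comparison does not use this rule and is unaffected. The change is worth making, but no primary conclusion depends on it.

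**What to change.** In PK-PD Model Fitting, replace the 20-point rule as follows:

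- Compare nested models that include a patient-level random effect on Ce50, using the likelihood-ratio statistic.
- Judge each covariate only by a p-value from permuting it across PD patients, for example p<0.01, with no separate fixed cut such as 6.63. Two criteria side by side could disagree.
- Report the UPDRS and MoCA coefficients with 95% confidence intervals whether or not they pass.
- Keep the analysis labelled exploratory, and state whether the same rule applies in Aim 3a.

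The cost is a few lines of text, a permutation run, and a false-positive rate of about 1% per covariate, against practically zero for the present rule in a patient-level fit. Recruitment, procedures and the primary comparison do not change.

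### Aims 1 and 3a: 58 recruits cover about 17% loss, not the stated 20%, on the 48 patients the power figure needs (minor)

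*Combined protocol and SAP*

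**What the plan says.** In section 4.a, under Sample Size, the Aim 1 paragraph describes a Monte Carlo power calculation. Its inputs come from earlier studies, which "suggest a 20% difference in Ce50 with 20% intersubject variability and an additive measurement error". The number per arm was raised until the power target was met: "N was then incremented until 80% power was obtained, which required approximately 24 patients per arm (total of 48 patients"). The allowance for loss follows: "To account for an estimated 20% dropout rate or protocol error, we plan to recruit a total of 58 subjects".

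The Aim 3a paragraph repeats the same calculation, the same 48, the same 20% and the same 58.

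Neither paragraph writes out the formula that leads from 48 to 58. The section gives no rule for replacing lost patients and no other margin, and the documents do not define which patients count as evaluable.

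**The concern.** A dropout rate is a share of the patients recruited. To finish with 48 after losing 20%, the number recruited must satisfy N × 0.8 ≥ 48. The stated 58 does not. As written, two of the four aims have a recruitment target that fails to deliver their own required number at their own assumed loss.

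The 80% figure has no slack to absorb this, because the plan stopped raising N once 80% was reached. At stake are the accuracy of the recruitment target and a small amount of power for the Ce50 comparisons. The design and the method of analysis are not affected.

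**Working it through.** **Inputs, all from section 4.a (Sample Size, Aims 1 and 3a) unless noted**

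- Required for 80% power: 24 per arm, 48 in total.
- Loss allowed for: 20%.
- Recruitment target: 58.
- Simulation repeats behind the power estimate: 1000.
- Criterion for the Ce50 comparison, from PK-PD Model Fitting (Aim 1): "Comparison of Ce₅₀ values between PD and ET populations will be made using 95% confidence limits on the resulting parameter fits". I read this as a two-sided 5% test. That is an assumption, since no alpha is stated for these aims.

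**Step 1. Reproduce the plan's figure.**
Multiplying: 48 × (1 + 0.20) = 57.6, rounded up to 58. Per arm: 24 × 1.2 = 28.8, rounded up to 29, and 2 × 29 = 58. Both match exactly.
Dividing: 48 / (1 − 0.20) = 60, or 30 per arm. This does not give 58.

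**Step 2. What 58 delivers at 20% loss.**
58 × 0.8 = 46.4, about 46 patients. Per arm: 29 × 0.8 = 23.2, about 23. The shortfall against 48 is 2 patients in each aim. This step does not depend on how 58 was obtained.

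**Step 3. What loss 58 can bear.**
(58 − 48) / 58 = 10 / 58 = 17.2%.

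**Step 4. Chance of keeping at least 48.**
If patients are lost independently, each with probability 0.20, the binomial probability of at least 48 remaining is 0.37 with 58 recruits and 0.58 with 60.

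**Step 5. Approximate effect on power.**
The plan's simulation cannot be rerun from the documents, because they do not give the size of the measurement error, the Hill coefficient or the exact success criterion. I therefore take 80% at 24 per arm as given and scale it with a normal approximation:

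power(n) = Φ[(1.960 + 0.842) × √(n / 24) − 1.960]

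At n = 24: Φ(0.842) = 80.0%.
At n = 23: Φ(2.802 × 0.979 − 1.960) = Φ(0.783) = 78.3%.

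The loss is about 1.7 percentage points.

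**Step 6. Compare with the precision of the plan's own estimate.**
With 1000 repeats, the Monte Carlo standard error at 80% is √(0.8 × 0.2 / 1000) = 0.0126, about 1.3 points. The 95% range is therefore about ±2.5 points.

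**The case against.** The strongest reply is that the gap is too small to matter. The required number is given only as approximate, the 20% is itself an estimate, and a drop of 1.7 points lies inside the simulation's ±2.5-point range. All of this stands, and it settles the severity as minor. It does not reconcile the figures: the plan fixes the total at 48 and inflates from 48.

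A second reply is that 46 is a worst case. The allowance covers protocol errors as well as dropout. Each patient gives responses and serum samples at several concentration steps, and these are fitted with a population model, so a patient with a shortened or faulty session might still contribute data. That is fair. The figure of 46 holds only if affected patients are wholly lost, and the documents do not say whether they would be.

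A third reply concerns Aim 3a. The Purpose section describes randomisation to induction with or without DBS. The Study Design section describes GPi against GPe stimulation, plus a comparison with off-stimulation patients from Aim 1. Which two groups make up the 48 is therefore unclear. The total of 60 follows from 48 by arithmetic, but a split of 30 per arm depends on settling that question first.

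Three stronger readings are tempting, and the documents do not support them:

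- **That Aims 2 and 3b show the correct rule in use.** They need 16 patients, and the plan says "we plan to recruit at least 20 subjects". This equals 16 / 0.8 = 20, but 16 × 1.2 = 19.2 also rounds up to 20. The number fits either rule, so it does not show that the plan used two different methods. Those two aims do reach their 16 at 20% loss.
- **That the plan is known to have multiplied by 1.2.** The exact match makes this likely, but no formula is written.
- **That 78% is the plan's own power at 23 per arm.** Only the anchor of 80% at 24 per arm comes from the plan. The rest is an approximation.

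**Conclusion.** The point holds, as a minor error. In both Aim 1 and Aim 3a, 58 recruits do not cover a 20% loss on 48 required patients. They cover 17.2%, and at 20% they leave about 46 if affected patients contribute nothing. Nothing elsewhere in the documents reconciles the figures.

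The size is two patients per aim and roughly 1.7 points of power. The shortfall in patients rests on total loss of affected patients. The power figure rests also on a two-sided 5% normal approximation and equal arms.

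A reader might infer that the two aims are materially underpowered. The documents do not support that: the estimated loss of power is within the Monte Carlo uncertainty of the target itself. The stated 24 per arm is taken as given here and has not been verified.

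**What to change.** Change the last part of the Aim 1 and Aim 3a sample-size paragraphs in one of two ways.

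1. **Keep 58 and describe it correctly.** State that 58 recruits cover about 17% loss. State also that at 20% loss about 46 evaluable patients (23 per arm) remain, with power slightly under 80%. Take the power value from a rerun of the existing simulation at 23 per arm. The 78% given here is a guide only.
2. **Set the target at 60.** Then 60 × 0.8 = 48. For Aim 3a, say which arms the 48 and the 60 refer to.

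Under either option, write out the inflation formula and say whether a patient with a protocol error counts as lost.

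The first option costs two reworded paragraphs and one simulation run. The second costs two more recruits per aim, four in all. Neither changes the design, the analysis or any clinical procedure. The targets for Aims 2 and 3b need no change on this account.
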